8.2.3 SAE Follow-up

Any follow up information to the SAEs should also be sent to Haihe Pharmacovigilance Team by using SAE Report Form stating that this is a follow-up to the previously reported SAE and reported to Haihe PV team within 24 hours in the same way as initial report. The follow-up information should include but not limit to whether the event has resolved or continues, if and how it was treated, and whether the patient continued or withdrew from study participation, et al.

The reported SAEs would be processed and assessed according to Haihe standard procedures by Haihe PV team. In order to assess SAE causality accurately, Haihe may require further information from the investigator in sending an urgent or a routine follow-up query. The investigator can

provide more follow-up information by replying to the query form or updating the SAE report form.

8.2.4 Serious and Unexpected Suspected Adverse Reaction

If an SAE is assessed by Haihe as unexpected according to the current version of Investigator's Brochure and there is a reasonable possibility that the Haihe study treatment cause the event, the case would fulfil the definition of 'Serious and Unexpected Suspected Adverse Reactions (SUSARs)'. All investigators involved in any study with HH2710 as investigational product, would be informed about the SUSARs cases, newly identified important safety issues or other safety documents, and relevant ethics committees/IRB would also be informed according to relevant requirements.

Haihe will submit Serious and Unexpected Suspected Adverse Reactions (SUSARs) and other safety information to the healthy authorities in accordance with national regulatory requirements in participating countries.

8.3 Reporting of Pregnancy

To ensure patient safety, each pregnancy occurring while the patient is on study treatment must be reported to Haihe within 24 hours upon investigator awareness. The pregnancy should be followed up to determine outcome, including spontaneous or voluntary termination, details of the birth, and the presence or absence of any birth defects, congenital abnormalities, or maternal and/or newborn complications.

Pregnancy should be recorded on a Haihe Clinical Trial Pregnancy Form and reported by the investigator to the Haihe Pharmacovigilance Team. Pregnancy follow-up should be recorded on the same form and should include an assessment of the possible relationship to the study treatment. Any SAE experienced during pregnancy must be reported on the SAE Report Form.

The consent from the female partner of male patients should be obtained before any information about the pregnancy is collected.

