 - Severe infections within 4 weeks prior to the first dose, including but not limited to hospitalization for complications of infection, bacteremia, or severe pneumonia.
 - Received therapeutic oral or IV antibiotics within 2 weeks prior to the first dose of study drug
16. Any important medical illness or abnormal laboratory finding that would increase the risk of participating in this study;
17. A history or current evidence/risk of retinal vein occlusion, central serous retinopathy or choroidneovascularization (CNV).
18. Concurrent therapy with any other investigational agent;
19. Concomitant malignancies or previous malignancies with less than 2 years disease-free interval at the time of enrollment; (But basal cell carcinoma skin cancer, cervical CIS(carcinoma in situ), CIS of the breast, localized or low Gleason grade prostate cancer, and < T2 bladder cancer can be included);
20. Current treatment with agents including vitamins, supplements, and herbal supplements that are metabolized solely through CYP3A4(See [Appendix 14.7](#));
21. Severe chronic obstructive pulmonary disease, severe asthma, pneumoconiosis, asbestosis and other occupational lung diseases.
22. A history of acute or chronic pancreatitis, surgery of the pancreas, or any risk factors that may increase the risk of pancreatitis;
23. Contraception (See [Appendix 4](#) Women of child-bearing age and contraceptive measures):

Patients who do not meet the following conditions will be excluded,

 - For women: Negative pregnancy test for females of child-bearing potential; must be surgically sterile, postmenopausal (defined as no menstrual cycle for at least 12 consecutive months), or compliant with an acceptable contraceptive regimen (2 highly effective forms, such as oral contraceptives, condom with spermicide, etc.) during and for 6 months after the treatment period. Abstinence is not considered an adequate contraceptive regimen;

- For men: Must be surgically sterile, or compliant with a contraceptive regimen (as above) during and for a minimum of 6 months after the treatment period.

6 Treatment

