7.1.5 Follow up period

7.1.5.1 Safety follow up

All patients must have safety follow up evaluations for 30 days, after the last dose of study treatment.

- Collection of AEs/SAEs, except for AEs/SAEs that occur after starting new antitumor treatment;
- ECG, Clinical lab test (blood routine, blood biochemistry, urine tests, thyroid function, and coagulation);
- New antitumor treatment and survival condition;
- Concomitant medication/treatment;
- Tumor evaluation will be continued in patients who discontinue treatment not for progressive disease until progressive disease, withdrawal of informed consent form, loss to follow-up, death or termination of study, whichever occurs first.

Follow-up of progressive disease

Patients who discontinue study treatment without disease progression will continue to receive a 6-week tumor assessment (CT or MRI) until malignant tumor progression and/or subsequent initiation of systemic anticancer therapy (whichever is earlier).

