8.2 Serious Adverse Event (SAE)

8.2.1 Definition of SAE

An adverse event is considered “serious” if it results in at least one of the following outcomes:

- Is fatal;
- Is life-threatening: refers to a reaction in which the patient was at risk of death at the time of the reaction; it does not refer to a reaction that hypothetically might have caused death if it were more severe;
- Requires inpatient hospitalization or prolongation of existing hospitalization;

Note that hospitalizations for the following reasons should not be reported as serious adverse events:

- Routine treatment or monitoring of the studied indication, not associated with any deterioration in condition;
- Elective or pre-planned treatment for a pre-existing condition that is unrelated to the indication under study and has not worsened since signing the informed consent;
- Social reasons and respite care in the absence of any deterioration in the patient’s general condition;
- Results in persistent or significant disability/incapacity;
- Constitutes a congenital anomaly/birth defect;
- Is medically significant, i.e., defined as an event that jeopardizes the patient or may require medical or surgical intervention to prevent one of the outcomes listed above;

Medical and scientific judgment should be exercised in deciding whether other situations should be considered serious reactions, such as important medical events that might not be immediately life threatening or result in death or hospitalization but might jeopardize the patient or might require intervention to prevent one of the other outcomes listed above. Examples of such events are intensive treatment in an emergency room or at home for allergic bronchospasm, blood dyscrasias or convulsions that do not result in hospitalization or development of dependency or abuse.

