8.2.2 Serious Adverse Event Reporting

To ensure patient safety, every SAE, regardless of suspected causality, occurring after the patient has provided main informed consent and until completion of the safety follow-up must be reported to Haihe Pharmacovigilance team within 24 hours upon the awareness of its occurrence.

Any SAEs experienced after the safety follow-up period should be reported to Haihe Pharmacovigilance team only if the investigator suspects a causal relationship to the study treatment.

Information about all SAEs is collected and recorded on HaiHe Serious Adverse Event Report Form; all applicable sections of the form must be completed in order to provide a clinically thorough report. The investigator must assess and record the relationship of each SAE to the study treatment, complete the SAE Report Form in English, and send the completed, signed form by e-mail within 24 hours to the Haihe Pharmacovigilance Team. For SAE causing the death, the investigator should provide the Autopsy report or related medical reports if available.

The e-mail address and contact information of HaiHe Pharmacovigilance Team, are listed in the investigator folder provided to each site. The original copy of the SAE Report Form and acknowledgement of receipt must be kept with the case report form documentation at the study site.

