14.4 Appendix 4 Women of child-bearing age and contraceptive measures

Women of child-bearing age refer to any women who have experienced menarche, not experienced surgical sterilization (hysterectomy or bilateral ovariectomy) and not yet reached menopause. Menopause refers to 12-month menostasis of women aged over 45 years in circumstance of lacking other biological or physiological causes. In addition, menopause can be confirmed only serum follicle-stimulating hormone (FSH) level in women aged below 55 years > 40 mIU/mL.

- Women receiving hormone replacement therapy (HRT) may have artificially inhibited FSH levels. Therefore, a wash-out period may be required to reach the physiological FSH level. The duration of wash-out period is associated with the functions of HRT. Wash-out duration recommended by the guideline is as follows. An investigator shall inspect serum FSH level at his or her discretion. If serum FSH level at any time of the whole wash-out period > 40 mIU/ml, the woman will be regarded as menopause:
 - At least one week of using vaginal hormone products (pessulum, ointment, gel)
 - At least four weeks of using transdermal products
 - At least eight weeks of using products for oral administration

Patients (including sexual partners of male patients) of child-bearing potential shall take full contraceptive measures and avoid donating eggs and sperms between the date of signing an informed consent form and month 6 after the last dose. Contraceptive measures acceptable in the study include: absolutely asexual life; intrauterine device (IUDs, e.g. Copper T); cervical cap (adding spermicidal cream or gel) plus male condom; diaphragm (adding spermicidal cream or gel) plus male condom or other two or more contraceptive measures. Patients will be provided with information on relevant acceptable contraceptive measures during patients' informed consent process.

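### Minor: Section 8.3 requires reports only of pregnancies on study treatment, although contraception is required until 6 months after the last dose; 5.3 #23 and Appendix 4 also disagree on contraception

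*Protocol*

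**What the plan says.** **Reporting.** Protocol 8.3 states that "each pregnancy occurring while the patient is on study treatment must be reported to Haihe within 24 hours upon investigator awareness". Its second paragraph names the form and the recipient, and adds "Any SAE experienced during pregnancy must be reported on the SAE Report Form". Its last sentence requires a female partner's consent before information on her pregnancy is collected.

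**Contraception window.** Criterion 23 in 5.3 requires contraception for women during treatment and for 6 months afterwards, and for men "during and for a minimum of 6 months after the treatment period". Appendix 4 puts the period "between the date of signing an informed consent form and month 6 after the last dose" and includes sexual partners of male patients.

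**SAE rules.** One SAE criterion in 8.2.1 is "Constitutes a congenital anomaly/birth defect". Under 8.2.2, every SAE is reported regardless of causality until safety follow-up is complete. After that, "Any SAEs experienced after the safety follow-up period should be reported to Haihe Pharmacovigilance team only if the investigator suspects a causal relationship". Section 7.1.5.1 sets the length of that follow-up: "All patients must have safety follow up evaluations for 30 days, after the last dose of study treatment".

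**Tests and contacts.** Section 7.2.1.5 requires a serum pregnancy test at the end-of-treatment visit. The later contacts are the 30-day safety follow-up and the 6-weekly tumour assessments for patients without progression (both 7.1.5.1), and the 3-monthly survival calls (7.1.5.2). None of them lists pregnancy.

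**The concern.** The protocol treats the 6 months after the last dose as a period in which pregnancy should be avoided. It does not require the investigator to report a pregnancy conceived in that period. The outcome could therefore be missed, including the normal outcomes that are needed to interpret any abnormal one. Section 11.3 tells women of child-bearing potential that the risk to a fetus is unknown, and pregnancy reports are one of the few ways to learn about that risk.

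The contraception rules raise a separate, smaller problem. Criterion 23 refers the reader to Appendix 4, so a site has to apply both texts, and on some points they give different answers.

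**Working it through.** There is no plan figure to reproduce. The check sets the rules side by side, and then looks at drug washout because it bears on how much the gap matters.

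**1. Windows, counted from the last dose (6 months taken as 180 days)**

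| Rule | Source | Ends |
|---|---|---|
| Pregnancy report | 8.3, first sentence | end of treatment (day 0) |
| Last scheduled pregnancy test | 7.2.1.5, Table 7-1 | end-of-treatment visit, within 7 days of last dose |
| All SAEs, any causality | 8.2.2, 7.1.5.1 | safety follow-up, day 30 (+7) |
| Suspected-related SAEs | 8.2.2 | no end stated |
| Contraception | 5.3 #23, Appendix 4 | month 6 (day 180) |

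Contraception without a pregnancy-reporting duty: 180 − 0 = 180 days. Part of this in which only suspected-related SAEs are reportable: 180 − 30 = 150 days, about 5 months.

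**2. What each kind of pregnancy triggers**

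- Conceived during dosing and found later: covered on a plain reading of 8.3, because the 24 hours run from investigator awareness.
- Conceived after the last dose, with an SAE by day 30: reportable as an SAE.
- Conceived after the last dose, with an SAE after day 30 (a birth defect, for example): reportable if the investigator suspects causality. The 8.3 sentence on SAEs during pregnancy has no time limit, but it sits among the rules for pregnancies that 8.3 already covers.
- Conceived after the last dose, ending in a normal birth or an uncomplicated termination: no route.

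**3. Existing contacts in the window**

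- Safety follow-up: one, at day 30 (+7).
- Tumour assessments: 180/42 = 4.3, so up to 4 (days 42, 84, 126 and 168), for patients without progression or new systemic therapy.
- Survival calls: 180/90 = 2 at most, assuming that calls start at about the last dose.

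Section 4.3 allows disease and survival follow-up to be left incomplete if enrolment stops early. The 30-day follow-up is then the contact to rely on.

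**4. Washout of parent drug**

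From the reported half-life (4.1), 8.42 to 10.9 h:

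- 5 × 8.42 = 42.1 h = 1.8 days
- 5 × 10.9 = 54.5 h = 2.3 days

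From the reported 3- to 4-fold accumulation (also 4.1), assuming a linear one-compartment model with R = 1/(1 − e^(−kτ)), so that t½ = τ·ln 2 / ln(R/(R − 1)):

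- BID (τ = 12 h): R = 3 gives 12 × 0.693/0.405 = 20.5 h; R = 4 gives 12 × 0.693/0.288 = 28.9 h
- QD (τ = 24 h): R = 3 gives 41.0 h; R = 4 gives 57.8 h
- Five half-lives: 5 × 20.5 = 103 h = 4.3 days, up to 5 × 57.8 = 289 h = 12.0 days

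Under this model the two reported figures do not agree, so the range to use is about 2 to 12 days. No human half-life is given for the metabolite HH3529.

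**5. Contraception definitions**

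| Point | 5.3 #23 | Appendix 4 |
|---|---|---|
| Abstinence | not adequate | acceptable |
| Methods | two highly effective forms | intrauterine device listed, no second method stated |
| Menopause | 12 months without a cycle | 12 months without a cycle, over 45, no other cause |

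**The case against.** **The two windows need not match.** Nothing in the documents says that reporting must last as long as contraception, and suspected-related SAEs stay reportable without limit. A reader might infer that birth defects after treatment go unreported altogether. The documents do not support that. What lacks a route is mainly normal births, uncomplicated terminations, and late SAEs judged unrelated.

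**The second paragraph of 8.3 has no time limit.** That is true, but it gives the form and route for the pregnancies that the first sentence defines. It does not clearly widen the scope.

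**On-treatment conceptions are handled.** This stands. One might infer that pregnancies begun on treatment are missed as well, but the end-of-treatment serum test and the clock from awareness cover them. The test cannot detect a later conception.

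**The drug is gone long before month 6.** For parent drug this stands even at 12 days. Genotoxicity tests were negative, and the reproductive-organ changes in animals recovered or showed a recovery trend (1.2.1.1.3). A reader should not infer fetal harm from this gap. The 6-month period is still the protocol's own choice.

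**Appendix 4 may simply be the fuller menopause definition.** This stands in part. The sentence on FSH in women under 55 is garbled: it could add a requirement or offer another way to confirm menopause. One might infer that a 43-year-old with 12 months' amenorrhoea must be classified differently by the two texts, but that depends on how the FSH sentence is read. The added age condition is clear. Reading Appendix 4 as a supplement does not resolve the abstinence conflict.

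**Conclusion.** The gap is real and of the lowest severity. For about 6 months after the last dose the protocol requires contraception but sets no reporting duty for a new pregnancy as such. For about 5 of those months only a suspected-related SAE is reportable. This rests on the plain wording of 8.3 and on finding no other pregnancy-reporting rule in either document. The Pregnancy Form and consent pages are not available, so what patients are told cannot be checked.

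The abstinence conflict and the other differences between criterion 23 and Appendix 4 are separate wording inconsistencies.

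No endpoint, analysis set or decision rule is affected. SAP section 7 says that the program is stopped, so a change would help only patients still within 6 months of their last dose, or a later protocol that reuses this text. The number of patients concerned cannot be derived from the documents.

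**What to change.** - **Section 8.3:** require reporting of any pregnancy in a patient, or in a consenting female partner of a male patient, from first dose until 6 months after the last dose. State that this includes conceptions during dosing that are found later.
- **Existing contacts:** ask about pregnancy at the 30-day safety follow-up and at any tumour assessment or survival call within the 6 months. At the 30-day visit, tell patients to report a pregnancy up to month 6, because later contacts may not take place.
- **Section 5.3 #23 and Appendix 4:** use one set of rules in both places for abstinence, number of methods and menopause. Rewrite the FSH sentence so that its role is clear. The choice of rule is the sponsor's.

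The cost is a sentence or two in 8.3, one question at visits and calls already planned, and one aligned definition. No visit or test is added. The downside is a little more pharmacovigilance work, including following each extra pregnancy to its outcome.

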8.4 Emergency unblinding of treatment assignment

This study is an open label study, therefore this section is not applicable.

8.5 Warnings and precautions

No evidence available at the time of the approval of this study protocol indicated that special warnings or precautions were appropriate, other than those noted in the provided Investigator's Brochure. Additional safety information collected between IB updates will be communicated in the form of Investigator Notifications. This information will be included in the patient informed consent and should be discussed with the patient during the study as needed.

8.6 Steering Committee

The steering committee (SC) will be established comprising investigators participating in the study.

The SC will ensure transparent management of the study according to the protocol through recommending and approving modifications as circumstances require. The SC will review protocol amendments as appropriate. Together with the clinical study team, the SC will also develop recommendations for publications of study results including authorship rules. The details of the role of the Steering Committee will be defined in a Steering Committee charter.

9 Data collection and management

9.1 Data confidentiality

Information about study patients will be kept confidential and managed under the applicable laws and regulations. Those regulations require a signed patient authorization informing the patient of the following:

- What protected health information (PHI) will be collected from patients in this study
- Who will have access to that information and why
- Who will use or disclose that information
- The rights of a research patient to revoke their authorization for use of their PHI.

In the event that a patient revokes authorization to collect or use PHI, the investigator, by regulation, retains the ability to use all information collected prior to the revocation of patient authorization. For patients that have revoked authorization to collect or use PHI, attempts should be made to obtain permission to collect follow-up safety information (e.g. has the patient experienced any new or worsened AEs) at the end of their scheduled study period.

The data collection system for this study uses built-in security features to encrypt all data for transmission in both directions, preventing unauthorized access to confidential participant information. Access to the system will be controlled by a sequence of individually assigned user identification codes and passwords, made available only to authorized personnel who have completed prerequisite training.

9.2 Data collection

The electronic case report form (eCRF) will be adopted for study data collection and management. Investigators shall timely, truthfully, completely record relevant data of each patient in the study. Information of all patients who has signed an informed consent shall be collected in the Case Report Form.

The sponsor or the data management party entrusted by the sponsor will provide the electronic data collection (EDC) system to study site. Relevant personnel will apply for corresponding account to login the EDC system after training. The investigator will enter the data generated in the study and follow the eCRF completion guideline. Finally, the principal investigator or personnel authorized shall sign an electronic signature for the confirmed data.

The Principal Investigator is responsible for assuring that the data entered into eCRF is complete, accurate, and that entry and updates are performed in a timely manner.

During the study, the PK/PD and biomarker specimens were collected by each site and then sent to the central laboratory designated by Haihe. Staff of the site will input the information required by the protocol in eCRF pages, and in the specimen information form of designated CRO. And the CRA (Clinical Research Associate) will review the eCRF to confirm the information is accurate and complete. Samples and/or data will be processed centrally and the results will be sent electronically to Haihe (or a designated CRO).

